#### **4.8.1. Adverse Events Variables**

The period of safety observation starts from the time when the patient gives informed consent and continues into the following periods:

- The pre-treatment period is defined from the day the ICF is signed to the day before the first dose of study treatment administration.
- The treatment-emergent adverse event (TEAE) period is defined from the day of the first study treatment administration to the day of the last study treatment administration + 168 days (24 weeks).
- The post-treatment period is defined from the day after the end of the TEAE period to the last study visit.

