### ***General common rules***

All safety analyses will be performed, unless otherwise specified, using the following common rules:

- Safety data in patients who do not belong to the safety analysis set (e.g., exposed but not enrolled) will be listed separately.
- The potentially clinically significant value (PCSV) values are defined as abnormal values considered medically important by the Sponsor according to predefined criteria/thresholds based on literature review and defined by the Sponsor for clinical laboratory tests and vital signs (PCSV version dated January 2009 [[Appendix 10.3](#)]).

Considering that the threshold defined in the PCSV list for monocytes and basophils can be below the ULN, the following PCSV criterion will be used for the PCSV analysis of monocytes and basophils:

- PCSV criterion for monocytes:  $>0.7$  Giga/L or  $>\text{ULN}$  (if  $\text{ULN} \geq 0.7$  Giga/L).
- PCSV criterion for basophils:  $>0.1$  Giga/L or  $>\text{ULN}$  (if  $\text{ULN} \geq 0.1$  Giga/L).
- PCSV criteria will determine which patients had at least 1 PCSV during the TEAE period, taking into account all evaluations including unscheduled or repeated evaluations.
- The treatment-emergent PCSV denominator by treatment group for a given parameter will be based on the number of patients assessed for that given parameter at least once during the TEAE period.

- All measurements, scheduled or unscheduled, fasting or not fasting, will be assigned to Global Analysis Windows defined in Appendix 10.2 /Table 1 in order to provide an assessment for the screening visit through follow-up visit time points.
- For quantitative safety parameters including central laboratory measurements and vital sign scores, descriptive statistics will be used to summarize observed values and change from baseline values by visit.

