### **5.8.3. Clinical Laboratory Measurements**

Clinical laboratory parameter actual values (quantitative) and change from baseline values will be descriptively summarized at baseline and each post-baseline visit for the study treatment period, by at least patient number, mean, median, Q1, Q3, SD, minimum and maximum.

Clinical laboratory parameters mean changes from baseline, with the corresponding SE, can be plotted at each visit in the case results warrant further investigation. These parameters will be presented by the biological functions defined in Section 4.8.2. For glucose, only fasting samples will be included in the summaries.

Individual patient laboratory parameter measurements will be additionally evaluated by PCSV criteria (See Appendix 10.3), specifically identifying patients with at least one post-baseline measurement that meets the PCSV criteria within the TEAE period. These laboratory parameters will be presented by the biological functions defined in Section 4.8.2. The incidence of PCSVs at any time during the TEAE period will be summarized regardless of the baseline level, and again according to the following baseline categories:

- Normal (according to PCSV criterion/criteria)/missing
- Abnormal according to PCSV criterion or criteria

Patient listings of laboratory measurements that meet PCSV criteria will be provided for the report appendix.

For those laboratory parameters that don't have an associated PCSV criteria, similar summary tables can be provided based on measurements outside the central laboratory normal ranges, if applicable.

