### 10.2. Windows for Analysis Time Points

Below are the definitions for the visit windows programmatically imposed on measures repeatedly collected over the course of the study. These visit windows reflect the study schedule of assessments as described in the protocol.

The visit windows are constructed using ranges applied to the number of days in study (study days) when the measure is collected. Below are the relevant definitions for the analysis visit windows:

1. Study day is defined as the number of days since the first study treatment administration +1. The first study treatment occurs on Day 1.
2. Since the protocol specifies that measurements be collected before study treatment is administered on a given day, it is appropriate that baseline include Day 1.
3. For randomized but not treated patients, Day 1 is the day of randomization.

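### The PCSV denominator in SAP 5.8 admits patients whose only value is the pre-dose Day 1 baseline, while the numerators require a post-baseline value

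*SAP*

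**What the plan says.** SAP 4.8.1 sets its safety periods by calendar day. The pre-treatment period runs "from the day the ICF is signed to the day before the first dose of study treatment administration". The TEAE period "is defined from the day of the first study treatment administration to the day of the last study treatment administration + 168 days". Neither definition uses clock time or a post-dose condition.

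SAP 6.1 takes baseline as the latest measurement before the first administration. SAP 10.2, item 2, notes that measurements precede dosing on a given day, so "it is appropriate that baseline include Day 1".

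The general common rules in SAP 5.8 then give two PCSV bullets:

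- Numerator: the criteria determine "which patients had at least 1 PCSV during the TEAE period, taking into account all evaluations including unscheduled or repeated evaluations".
- Denominator, for each parameter: it "will be based on the number of patients assessed for that given parameter at least once during the TEAE period".

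The parameter sections are narrower on the numerator. SAP 5.8.3 speaks of "identifying patients with at least one post-baseline measurement that meets the PCSV criteria within the TEAE period", and 5.8.4 (vital signs) and 5.8.5 (ECG) use the same condition. None of the three restates the denominator.

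**The concern.** The numerator and denominator of one percentage should be drawn from the same patients. Here the numerator is limited to patients who could show a post-baseline abnormality. The denominator accepts anyone with a value dated on or after the day of first dose, and the baseline value itself meets that condition. A patient never tested again for a parameter would be counted as tested and free of abnormality. The error lowers reported abnormality rates, which is the non-conservative direction for safety tables. It matters most for parameters with few post-dose samples, in a study that the SAP overview says was discontinued early.

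**Working it through.** No figure in the plan rests on this rule, so there is none to reproduce. The check sets the definitions side by side, adds date arithmetic, and then works through the dilution.

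**1. Is the Day 1 baseline inside the TEAE period?**
The pre-treatment period ends the day before first dose, and the TEAE period starts on the day of first dose (SAP 4.8.1). Blood is drawn before dosing and the ECG is done before the blood draw (SAP 10.4.1.1, footnotes 5 and 8). Both are scheduled on Day 1. By date they lie in the TEAE period; by SAP 6.1 they are baseline. Nothing in either document excludes them from what counts as assessed.

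**2. What happens to a patient with only that value?**
Denominator (5.8): one assessment in the TEAE period, so the patient is in. Numerator (5.8.3 to 5.8.5): a post-baseline value is needed, so the patient cannot be in. The patient is counted as having no PCSV.

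**3. Which parameters are exposed?** (SAP 10.4, Tables 2 and 3)

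| Parameter | Scheduled after the first infusion |
|---|---|
| Vital signs | Day 1 post-infusion and every later visit |
| Chemistry | Weeks 4, 8, 16 and onward |
| Hematology | Weeks 52 and 72 only |
| ECG | Week 72 (V17) only |

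Vital signs and chemistry are barely touched. Hematology and ECG are exposed.

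**4. Do the late visits fall inside the TEAE period?**
TEAE end = day of last dose + 168.

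- *Fully dosed patient.* The last dose is on Day 337, so the period ends on Day 337 + 168 = 505. Week 52 hematology (Day 365) is inside. V17 is Day 505 ± 7, that is Days 498 to 512. Days 506 to 512, 7 of the 15, fall outside, so even a completer's only scheduled post-dose ECG can miss the period.
- *Patient who stops drug but stays on the visit schedule* (as Protocol 8.3.2 encourages). Week 52 hematology is inside only if last dose + 168 ≥ 365, that is, last dose on or after Day 365 − 168 = 197. With a last dose at Week 24 (Day 169) the period ends on Day 337, before both Day 365 and Day 505.
- *Patient who withdraws from the study.* Protocol 8.3.2 and 9.1.2 ask for an early termination visit with the end-of-DBTP assessments, which include hematology. Off-drug follow-up of at least 20 weeks after last dose then ends with V17 (hematology and ECG). Twenty weeks is 20 × 7 = 140 days, within 168.

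**5. How large is the dilution?**
Let N be the patients in the denominator as written, m those of them with a post-baseline value, and x those with a PCSV. Then

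reported rate = x/N = (x/m) × (m/N).

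The documents give neither N nor m. With x/m assumed to be 20%:

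| m/N (assumed) | Reported rate |
|---|---|
| 1.00 | 20% |
| 0.90 | 0.20 × 0.90 = 18% |
| 0.70 | 0.20 × 0.70 = 14% |
| 0.50 | 0.20 × 0.50 = 10% |

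**The case against.** The strongest reply is that the authors plainly meant post-baseline patients in both places. The bullet concerns a treatment-emergent denominator, SAP Table 1 places Day 1 measurements before first treatment, and all three numerators already say post-baseline. That may well be the intent. The denominator bullet does not say it, and a literal program would include the Day 1 value.

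Second, patients who leave early are not simply lost. The early termination visit and off-drug follow-up described above should supply hematology and, at V17, an ECG, and unscheduled values also count. This stands, and it means the affected share may be small. It is weakened a little by labelling: Protocol 9.1.2 and SAP 10.4.2 call the end-of-DBTP visit visit 16, whereas the schedule numbers Week 52 as V15, and V16 (Week 62) has neither hematology nor ECG.

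Third, the consequence is modest. Safety is descriptive without testing (SAP 5.8), patients meeting PCSV criteria are listed individually, and the by-visit laboratory summaries show how many patients were measured. This also stands.

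Three stronger readings are tempting, and the documents do not support them:

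- *Pre-dose abnormalities are reported as treatment-emergent.* A reader could infer this from the general numerator bullet, which takes in all evaluations. But the common rules yield where another section specifies otherwise, and 5.8.3 to 5.8.5 do specify a post-baseline value.
- *Every patient enters every denominator.* Only treated patients with a Day 1 measurement of that parameter are drawn in by this route. One whose baseline comes from screening alone is not.
- *The rule creates a false difference between arms.* That would need unequal post-dose testing. The trial is randomized and blinded and was stopped for poor recruitment, and nothing in the documents suggests an imbalance.

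**Conclusion.** The point holds for the denominator. As written, a treated patient whose only TEAE-period value for a parameter is the pre-dose Day 1 baseline counts as assessed and as free of a PCSV, and the reported incidence shrinks by the factor m/N. The effect is confined mainly to hematology and ECG percentages. Its size is unknown: the percentages in the dilution table rest on assumed values of m/N and an assumed 20% rate. That m/N is low because the study stopped early is an inference the documents do not establish. No hypothesis test or efficacy result is affected. This is a small, clear mismatch in a descriptive safety table, worth correcting because the correction costs almost nothing.

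**What to change.** In the SAP 5.8 denominator bullet, count only patients with at least one post-baseline assessment of the parameter during the TEAE period, with post-baseline defined as taken after the start of the first infusion. That definition keeps the Day 1 post-infusion vital signs. A period starting the day after first dose, as Protocol 11.4.5.2 uses for quantitative laboratory and vital sign summaries, would lose them.

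Adding the same word to the general numerator bullet is optional tidying: it only aligns that bullet with 5.8.3 to 5.8.5.

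The cost is one phrase in the SAP and one programming flag, with no new data. Denominators become slightly smaller and reported rates slightly higher.

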8.3.2.1. Reasons for Permanent Discontinuation of Study Drug

Study drug dosing will be permanently stopped in the event of:

- Evidence of pregnancy
- Severe, acute infusion reactions related to study treatment including, but not limited to, anaphylaxis
- Specific types of liver dysfunction (eg, Hy's law is met ([Guidance for Industry Drug Induced Liver Injury: Premarketing Clinical Evaluation FDA 2009]))

Liver impairment as evidenced by 1 or more of the following criteria and no other reason can be found to explain the following lab abnormalities, such as viral hepatitis A, B, or C; pre-existing or acute liver disease; or another drug capable of causing the observed injury:

- ALT or AST $>8 \times$ ULN, or
- ALT or AST $>5 \times$ ULN for more than 2 weeks, or
- ALT or AST $>3 \times$ ULN and total bilirubin $>2 \times$ ULN (or international normalized ratio [INR] >1.5)
- ALT or AST $>3 \times$ ULN with the appearance of fatigue, nausea, vomiting, right upper quadrant pain or tenderness, fever, rash, and/or eosinophilia ($>5\%$)
- Patient withdraws consent

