9.2.3.4. Laboratory Testing

Hematology, chemistry, and serum pregnancy testing samples will be analyzed by a central laboratory. Urine pregnancy testing samples will be analyzed locally (patients will use a pregnancy test provided by the site for phone visits in the follow-up). Detailed instructions for blood sample collection are in the laboratory manual provided to study sites.

Samples for laboratory testing will be collected at visits according to [Table 1](#) and [Table 2](#). Tests will include:

Blood Chemistry

Sodium	Total protein, serum	Total bilirubin
Potassium	Creatinine	Uric acid
Chloride	Blood urea nitrogen (BUN)	Creatine phosphokinase (CPK)
Carbon dioxide	Aspartate aminotransferase (AST)	Phosphorus
Calcium	Alanine aminotransferase (ALT)	Magnesium
Glucose	Alkaline phosphatase	
Albumin	Lactate dehydrogenase (LDH)	

Note: Blood chemistry should be performed after the patients have fasted for at least approximately 8 hours at the visits defined in the Schedule of Events.

Hematology

Hemoglobin	Differential:
Hematocrit	Neutrophils
Red blood cells (RBCs)	Lymphocytes
White blood cells (WBCs)	Monocytes
Red cell indices	Basophils
Platelet count	Eosinophils

Other Laboratory Tests

- Pregnancy testing (WOCBP only): serum human chorionic gonadotrophin (β -HCG) pregnancy testing at screening, and urine pregnancy testing at all subsequent scheduled visits
- Pregnancy testing and contraception are not required for women with documented hysterectomy or tubal ligation.
- Postmenopausal women must be amenorrheic for at least 12 months in order not to be considered of childbearing potential. Follicle-stimulating hormone will be measured for verifying postmenopausal status, as applicable.
- Blood sample for FT4 and TSH

Abnormal Laboratory Values and Laboratory Adverse Events

All laboratory values must be reviewed by the investigator or authorized designee.

Significantly abnormal test results that occur after start of treatment must be repeated to confirm the nature and degree of the abnormality. When necessary, appropriate ancillary investigations should be initiated. If the abnormality fails to resolve or cannot be explained by events or conditions unrelated to the study medication or its administration, the medical/study director must be consulted.

The clinical significance of an abnormal test value, within the context of the disease under study, must be determined by the investigator.

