11.4.5.2. Other Safety

Definitions

The following definitions will be applied to laboratory parameters and vital signs:

- The potentially clinically significant value (PCSV) criteria are defined as abnormal values considered medically important by the sponsor according to predefined criteria/thresholds based on literature review and defined by the sponsor for clinical laboratory tests and vital signs. Potentially clinically significant value criteria will be provided in the SAP.
- PCSV criteria will determine which patients had at least 1 PCSV during the TEAE period, taking into account all evaluations performed including unscheduled or repeated evaluations. The number of all such patients will be the numerator for the PCSV percentage.
- The treatment period used for the quantitative analysis of laboratory and vital sign data is defined from the day after the first dose of double blind study treatment to the day of the last dose of double-blind study treatment + 28 days.

Analysis

Summary statistics of all laboratory variables (including lipid HDL-C) and all vital sign parameters (raw data and changes from baseline) will be calculated for each protocol-scheduled visit assessed during the respective treatment periods. For selected parameters, mean changes from baseline with the corresponding SE may be plotted over time in each treatment group.

The incidence of PCSVs at any time during the respective TEAE periods will be summarized regardless of the baseline level, and again according to the following baseline categories:

- Normal/missing
- Abnormal according to PCSV criterion or criteria

For laboratory parameters for which a PCSV criterion is not defined, similar table(s) using the normal range will be provided, regardless of baseline level.

Listings will be provided with flags indicating the laboratory values meeting PCSV criteria.

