#### **6.5. Unscheduled Assessments**

For efficacy, safety laboratory data, vital signs, ECG, unscheduled visit measurements may be used to provide a measurement for a time point, including baseline, if appropriate according to their definitions. The measurements may also be used to determine abnormal values, AESIs, and PCSVs.

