**Table 1: Global Analysis Windows**

Visit label	Targeted Study Day	Analysis Window in Study Day
Screening	< Day 1	Measurement obtained prior to first study treatment, and not defined as baseline visit
Day 1	1	Measurement obtained closest to first study treatment, while remaining prior to first study treatment
Week 4	29	15 to 42
Week 4K, where K=2,3,...13	28K+1	15+28*(K-1) to 42+28*(K-1)
FU – W10	435	379 - 470
FU – W20	505	> 470
Study days are calculated from the day of first study treatment administration, the day of first study treatment administration being Day 1.		

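### By-visit laboratory tables include rows that only non-routine draws can fill: 5 of 13 Week 4-52 windows for chemistry and 12 of 13 for hematology

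*SAP*

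**What the plan says.** The general rules in SAP 5.8 say that "All measurements, scheduled or unscheduled, fasting or not fasting, will be assigned to Global Analysis Windows defined in Appendix 10.2". SAP 6.5 repeats the permission: "unscheduled visit measurements may be used to provide a measurement for a time point, including baseline, if appropriate according to their definitions". SAP 5.8.3 says that laboratory values and changes from baseline "will be descriptively summarized at baseline and each post-baseline visit for the study treatment period", with optional plots of mean change. Table 1 in SAP Appendix 10.2 has one set of windows for all parameters, every 4 weeks from Week 4 to Week 52, followed by two follow-up windows.

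The schedule of events (Protocol Tables 1 and 2; SAP Tables 2 and 3) is sparser:

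- After baseline, chemistry is drawn at Weeks 4, 8, 16, 24, 32, 40, 48, 52, 62 and 72.
- After baseline, hematology is drawn at Weeks 52 and 72 only.

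Protocol 11.4.5.2 is narrower than the SAP. There the summary statistics "will be calculated for each protocol-scheduled visit assessed during the respective treatment periods". SAP 1.2.4, which lists the modifications from the protocol, does not mention a change on this point.

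**The concern.** A by-visit table is read down the column, on the understanding that each row describes roughly the same patients, sampled for the same reason. Here some rows would come from routine sampling of everyone still attending, and others only from patients who had a reason for an extra draw. One such reason depends on the result itself, since Protocol 9.2.3.4 says: "Significantly abnormal test results that occur after start of treatment must be repeated to confirm the nature and degree of the abnormality". Under Protocol 10.1.3 a rise in ALT or AST is also an adverse event of special interest, and Protocol 10.1.1 asks for such events to be followed until resolved or clinically stable.

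The hypothesis tests and planned efficacy analyses have been dropped, so descriptive safety tables are a main output of the abbreviated report. With few patients enrolled, one retested patient could make up a whole row.

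**Working it through.** **Windows.** Table 1 gives Week 4K the range 15 + 28(K-1) to 42 + 28(K-1), which is 28K-13 to 28K+14, around the target day 28K+1.

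- K=1 gives Days 15-42, K=2 gives 43-70, K=3 gives 71-98, and so on to K=13, which gives 351-378.
- This reproduces the stated Week 4 row and meets the follow-up window that starts on Day 379.

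**Can a scheduled draw fill an unscheduled row?** The target lies 14 days after the window opens and 13 days before it closes. With the ±4-day visit window, every on-time draw stays in its own row. It would have to be at least 14 days late or 15 days early to land elsewhere.

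**Count of Week 4-52 rows.**

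| | Scheduled | No scheduled draw | Share |
|---|---|---|---|
| Chemistry | 4, 8, 16, 24, 32, 40, 48, 52 | 12, 20, 28, 36, 44 | 5/13 = 38% |
| Hematology | 52 | 4 to 48 | 12/13 = 92% |

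Hematology also has no scheduled draw for the first follow-up row (Week 62).

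**What can enter the unscheduled rows?**

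- *Late chemistry retests.* After an on-target draw on Day 28K+1, a retest enters the next window from Day 28K+15, that is 14 days later, or 10 days later if the draw was 4 days late. One liver criterion in Protocol 8.3.2.1 is ALT or AST above 5 times "ULN for more than 2 weeks". Confirming it takes a value at least 15 days on. From the draws on Days 57, 113, 169, 225 and 281 that means Days 72, 128, 184, 240 and 296, which fall in the Week 12, 20, 28, 36 and 44 windows (71-98, 127-154, 183-210, 239-266, 295-322). These are exactly the five rows with no scheduled chemistry.
- *Prompt chemistry retests.* These stay in the scheduled row, where SAP 6.4 takes the value nearest the target day.
- *Hematology.* No scheduled on-treatment result before Week 52 exists to trigger a retest. These rows would hold for-cause or early-termination draws.
- *Early-termination and later visits.* These fall on any study day and need not follow an abnormal result. Protocol 11.4.5.2 ends the quantitative laboratory analysis 28 days after the last dose. SAP 5.8.3 refers only to the study treatment period and does not restate that limit, so it is open whether post-termination draws count.

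**Illustration of size (all inputs assumed).** Take a standardized test with within-patient correlation 0.7, a retest when a value exceeds 1.96 SD, and no drug effect.

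- *Abnormality does not persist.* The mean of values above the trigger is 2.34 SD, so the retest averages 0.7 × 2.34 = 1.64 SD above the population mean. The same patients' baseline averages 1.63 SD, so their change from baseline is about 0.00 to 0.01 SD. The observed-value row is high and the change row is not.
- *Abnormality persists as a 1 SD shift for reasons unrelated to the drug.* Mean change in the row is about 0.10, 0.25, 0.50 or 1.0 SD when retests make up 10%, 25%, 50% or 100% of it.

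**The case against.** The best defense is that the SAP need not be read this way. Protocol 11.4.5.2 refers to protocol-scheduled visits, SAP 1.2.4 lists no departure from it, SAP 6.4 says the windows represent the assessment schedule, and SAP 6.5 allows unscheduled values only where appropriate. A careful programmer might suppress the extra rows. That stands as a reason to expect the problem may not appear, but no SAP sentence requires it and the SAP 5.8 rule points the other way.

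It is also true that the summaries are descriptive, patient numbers are shown, plots are optional, and the PCSV counts already use every evaluation. All of this limits the consequence.

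A reader might infer more than the documents support:

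- *That the unscheduled rows hold mainly abnormal-result retests.* No retest interval is given, prompt retests stay in the scheduled row, and Protocol 9.1.3 allows unscheduled visits for any reason. In a study stopped administratively, early-termination visits may supply many of the values. For hematology the retest route is absent before Week 52.
- *That the tables will show false rises.* The documents give no number or direction for unscheduled values. The change from baseline may be near zero, as above, and low-side abnormalities would pull means down. A persisting elevation is real in that patient. What misleads is reading it as the group's mean.

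**Conclusion.** The defect is real but modest. As written, 5 of 13 Week 4-52 rows for chemistry and 12 of 13 for hematology can be filled only by non-routine draws, and their means and changes should not be compared with the scheduled rows. This follows from Table 1 and the schedule of events, assuming visits take place within their windows. For ALT and AST the follow-up triggers respond to increases, and a significantly high CPK must also be repeated. Those rows can therefore look raised with no drug effect. How large the distortion is, and whether it occurs at all, cannot be determined from the documents; the SD figures only illustrate the mechanism. The consequence is confined to by-visit means, changes and plots. PCSV counts, the eDISH plot and the listings are not affected.

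**What to change.** In SAP 5.8.3 and Appendix 10.2, limit by-visit laboratory summaries and plots, parameter by parameter, to windows with a scheduled draw:

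- chemistry: Weeks 4, 8, 16, 24, 32, 40, 48 and 52, FU-W10 and FU-W20;
- hematology: Week 52 and FU-W20.

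This brings the SAP into line with Protocol 11.4.5.2. Within these windows, prefer the scheduled value, as an exception to the nearest-day rule in SAP 6.4. Show early-termination values in a separate row for early termination or last on-treatment value. Without it the restriction would remove those draws from the by-visit summaries, and in a study stopped early they may be much of the on-treatment hematology. Keep all unscheduled values in the PCSV tables, the eDISH plot and the listings.

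One cross-reference must be reconciled at the same time. The early-termination text (Protocol 9.1.2, SAP 10.4.2) equates visit 16 with Week 52, while the schedule has Week 52 as visit 15, and visit 16 carries no hematology. This decides whether patients who leave early contribute a hematology value.

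The cost is one or two SAP sentences and a parameter-by-window table in the programming specification. The small downside is that unscheduled values between scheduled draws no longer appear in the by-visit means.
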